5.2.2 Daily product consumption

Number of daily product (HeatSticks, cigarette, other heat not burn products, e-cigarettes, smokeless tobacco pipe, smokeless tobacco, cigars/pipes/kiseru/shisha and nicotine replacement therapy) usage will be defined as an average of total consumption of each product (see 5.2.1) divided by the number of days from randomization until last reported monthly product use.

Confidentiality Statement

Data and information contained in this document are considered to constitute trade secrets and confidential commercial information, and the legal protections provided to such trade secrets and confidential information are hereby claimed under the provisions of applicable law. No part of this document may be publicly disclosed without the written consent of Philip Morris Products S.A

$$\left[\text{Daily product consumption} = \frac{\text{Total product consumption}}{\text{Total number of days}} \right]$$

where i is the month where product use was recorded.

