### 12.3 Product use

[figure not shown]
Although patients are being requested to use solely the product allocated to their respective study arm, it is considered that not all patients randomized to the IQOS arm or to continue smoking cigarettes will exclusively use the randomized product at all times during the study. Patients may concomitantly use IQOS and cigarettes (dual-use). To assess dual use of IQOS and cigarettes, PMI has defined categories of pattern of product use.

Product use pattern categories will be specified based on the average number of product used per month of each category (i.e., Marlboro HeatSticks or smoked cigarettes) as self-reported in the product use questionnaire over the study duration. Further determinants, such as percentages of the respective products, or numbers of other nicotine-containing products may be used, and will be provided in the SAP.

Actual product use pattern categorization is described in Figure 3. Primary analysis will consider only those patients who used only HeatSticks and/or cigarettes. Those who used other nicotine-containing products (e.g., e-cigarettes) will be considered in a separate category, "Other" (not represented in Figure 3). More granular product exposure categories may be used for the detailed description of the product use patterns observed in the study. Full details of the product use categories will be reported in the SAP.

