5.2 Product Use

The number of Cigarettes, Heatsticks, and other nicotine/tobacco containing product used daily, as reported by the patient and collected in the electronic diary, will be used to monitor product use and evaluate adherence to product allocation.

Patients will be classified according to their monthly actual product use pattern into four categories: cigarette users; IQOS user, dual user, or other as described in Figure 2. “Other” will include the following products: Other heat not burn products, e-cigarettes, Smokeless Tobacco Pipe, Smokeless Tobacco, Cigars/Pipes/Kiseru/Shisha, and Nicotine Replacement Therapy.

The calculation of the monthly product use to classify patients into the four categories is described in section 5.2.3

Confidentiality Statement

Data and information contained in this document are considered to constitute trade secrets and confidential commercial information, and the legal protections provided to such trade secrets and confidential information are hereby claimed under the provisions of applicable law. No part of this document may be publicly disclosed without the written consent of Philip Morris Products S.A

[figure not shown]

Figure 2: Product Use Categories

Abbreviations: HS, Marlboro HeatSticks; cig, cigarette

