5.2.3 Monthly product consumption

Number of monthly product (HeatSticks, cigarette, other heat not burn products, e-cigarettes, smokeless tobacco pipe, smokeless tobacco, cigars/pipes/kiseru/shisha and nicotine replacement therapy) usage will be defined the daily average (see 5.2.2) multiplied by 30.

$$\left[\text{Monthly product consumption} = 30 * \frac{\text{Total product consumption}}{\text{Total number of days}} \right]$$

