5.2.4 Percentage for specific product consumption for dual-users

Percentage for specific product consumption (HeatSticks and cigarettes) will be defined as total consumption of the specific product divided by all product consumption (excluding all other products) from post randomization until date of last self-reported product use.

$$\left[\begin{aligned} &\text{Percentage for specific product consumption to all product consumption (\%)} \\ &= \frac{\text{Total consumption of a given product}}{\text{Total consumption of Heatsticks and cigarettes}} \end{aligned} \right]$$

5.2.5 Average cigarette consumption at V3 and V4.

For each patient regardless of randomized arm, the average daily cigarette consumption at V3 and V4 will be calculated. This will be done as described in section 5.2.2 except that total consumption up to each visit and days elapsed since randomization will be used.

$$\left[\text{Daily product consumption at } V_i = \frac{\text{Total product consumption until } V_i}{\text{Total number of days until } V_i} \right], i = 3, 4$$

where V_3 is Visit 3 and V_4 is Visit 4.

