9.1.4 Definitions for Statistical Data Analysis

For periodontal parameters:

Six sites per tooth are to be evaluated. At least 4 of the 6 sites per tooth must be evaluated and have the measurements recorded for the tooth to be included in the assessment. If the site is evaluated and there is no PD to measure, the site must be recorded as 0 to indicate that there was no PD at the site (and to distinguish it from a site that was not evaluated).

When less than 4 sites are recorded, the assessment of the tooth will be considered as missing, and all periodontal assessments for that tooth will be excluded from the calculation of the means over all teeth (see Section 5.1.1).

For BoExp parameters:

Values below the lower limit of quantification (LLOQ) will be imputed using LLOQ/2. For

Confidentiality Statement

Data and information contained in this document are considered to constitute trade secrets and confidential commercial information, and the legal protections provided to such trade secrets and confidential information are hereby claimed under the provisions of applicable law. No part of this document may be publicly disclosed without the written consent of Philip Morris Products S.A.

values above the upper limit of quantification (ULOQ), the ULOQ will be imputed.

The number of values below LLOQ or above ULOQ will be presented in each summary table. If more than 50% of the data are below LLOQ, only the number and percentage of values below LLOQ will be reported in the summary together with the minimum and maximum values.

For calculation of creatinine adjusted BoExp if the denominator is below LLOQ then the ratio will not be calculated and will be tabulated as “Not Calculated” in descriptive summaries and excluded from the main analysis.

For self-reported tobacco or nicotine containing tobacco product use over the duration of the study data:

Only available data will be included in the product use summaries. Overall product exposure groups will be defined based on the data collected from randomization until EOS.

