9.5.1.1 Primary Analyses

Primary Analysis of Change from Baseline in PD at V4	
Population	
 • As Exposed Set For this analysis, subjects categorized in IQOS user, cigarette user or dual user will be included with initial PD \geq 4mm will be included.
	The primary analysis will be performed on the As Exposed Set using a mixed model for repeated measurements (MMRM). Estimates of difference in PD will be calculated for Cigarette User against IQOS User categories and Cigarette User against Dual User categories. The model will include the PD change from baseline as the dependent variable, adjusting for the following covariates; 
 1. Daily cigarette consumption at V1 2. Disease severity at V1 3. Full mouth PD at V1 4. Visit 5. Product use pattern (IQOS user, cigarette smoker or dual user) 6. Interaction between visit and product use

Confidentiality Statement

Data and information contained in this document are considered to constitute trade secrets and confidential commercial information, and the legal protections provided to such trade secrets and confidential information are hereby claimed under the provisions of applicable law. No part of this document may be publicly disclosed without the written consent of Philip Morris Products S.A

Primary Analysis of Change from Baseline in PD at V4

7. Average daily cigarette use at each visit
8. Interaction between Daily cigarette consumption at V1 and product use
9. Interaction between Disease severity at V1 and product use
10. Time since last SRP
11. Number of target tooth/teeth extracted
12. Number of non-measured target tooth/teeth extracted
13. Baseline tooth mobility

Site will be included as a random effect. The degrees of freedom will be adjusted by using Kenward Roger (KR) method. A Toeplitz structure (“type=toep”) will be specified as the covariance matrix. However, other covariance structures may be used in case of non-convergence. Covariates 8-12 will be assessed for adequacy in the model using a step-wise (backward) approach through the following algorithm.

1. Fit a full model using maximum likelihood with all covariates
2. Perform a likelihood ratio test for the full model and drop the covariate with the largest p-value for the likelihood ratio statistic if it is more than 0.05.
3. Drop one covariate (only covariates 7-14) and re-fit the model.

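### A monthly product-use questionnaire missing before a later one counts as zero use in the rate that sets the primary As Exposed groups (SAP 5.2.2)

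*SAP*

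**What the plan says.** SAP 5.2.1 defines total consumption as a sum over the post-randomisation monthly questionnaires (called forms below), with the index running over recorded months. SAP 5.2.2 turns that total into a daily rate: it is "divided by the number of days from randomization until last reported monthly product use". The 5.2.2 formula shows its denominator only as a total number of days. It is followed by "where i is the month where product use was recorded", although the formula contains no index i.

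Under SAP 5.2.3, monthly use "will be defined the daily average (see 5.2.2) multiplied by 30". The opening of SAP 5.2 ties this figure to the grouping: "The calculation of the monthly product use to classify patients into the four categories is described in section 5.2.3". Protocol 12.3 gives the same basis: "Product use pattern categories will be specified based on the average number of product used per month of each category".

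The resulting category defines the groups in the As Exposed Set (SAP 8.1) and is covariate 5 in the primary MMRM (SAP 9.5.1.1). For missing product-use data, SAP 9.1.4 says "Only available data will be included in the product use summaries" and adds that the exposure groups rest on data from randomisation to end of study.

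SAP 5.2.5 derives daily cigarette use at V3 and V4, which is covariate 7, in the same way except that "total consumption up to each visit and days elapsed since randomization will be used".

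**The concern.** Numerator and denominator cover different periods. When a form is missing and a later one exists, its use drops out of the total but its days stay in the day count. Arithmetically this imputes zero use for that month. Nothing in either document deducts those days, imputes the missing form or otherwise defines the day count.

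At stake is the grouping behind the primary test. Protocol 12.3 bases the categories on numbers of product per month, and a count is what a wrong day count distorts. A dual user whose less-used product is just above a cut-off could be computed below it and placed in a single-product group. If dual users respond somewhere between the two pure groups, that blurs the IQOS-versus-cigarette contrast.

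**Working it through.** The plan gives no worked value for this rate, so there is no figure to reproduce first.

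**Inputs**
- Numerator: use on recorded forms only (SAP 5.2.1).
- Denominator: all days from randomisation to the last report (SAP 5.2.2 prose).
- Month of 30 days (Protocol 4.3 and 7.5.7), so six forms run to day 180.
- V1 is 7 to 14 days before V2 (Protocol 9.1 and 9.2).
- Assumptions: constant true use, and each form holds a 30-day total.

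**Formula.** Computed rate / true rate = 30 × (forms received) / (days from randomisation to last report).

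**Day count from V2**

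| Situation | Calculation | Ratio |
|---|---|---|
| All six forms, last report day 180 | 180/180 | 1.00 |
| One earlier gap, last report day 180 | 150/180 | 0.83 |
| Two earlier gaps, last report day 180 | 120/180 | 0.67 |
| One gap, last report at month 5, 4 or 3 | 4/5, 3/4, 2/3 | 0.80, 0.75, 0.67 |
| Only Month 6 missing, so last report day 150 | 150/150 | 1.00 |

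The error arises only from a gap before the last report.

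**Day count from V1.** Protocol 6.3 and SAP 2.1.1 and 4.3.1 place randomisation after the V1 assessments; Protocol Table 4 and Appendix 1 place it at V2. From V1, day 180 becomes day 187 to 194:
- complete data: 180/187 = 0.96 to 180/194 = 0.93
- one gap: 150/187 = 0.80 to 150/194 = 0.77

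**Who could change group.** For a count cut-off C, a true rate up to C/(150/180) = 1.2C with one gap, or C/(120/180) = 1.5C with two, computes at or below C. The cut-offs are in SAP Figure 2, which is not visible. Under assumed cut-offs of 10, 30 and 60 per month, the upper limits are 12, 36 and 72 (one gap) and 15, 45 and 90 (two gaps).

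**What is not affected.** In the SAP 5.2.4 percentages the days do not enter. The FAS and PP groups follow the randomised product (SAP 8.2, 8.3).

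**SAP 5.2.5 (covariate 7), day count from V2.** The denominator runs to the visit, so a missing final form also counts as zero:
- V4 at day 180, Month 6 missing: 150/180 = 0.83
- V3 at day 90, Month 3 missing: 60/90 = 0.67

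Protocol 7.5.7 allows a Month 3 form to be completed after V3 and brought to the next visit. SAP 5.2.5 does not say whether it then counts towards V3. If it is left out and V3 falls on day 83 to 89, the ratio is 60/83 = 0.72 to 60/89 = 0.67.

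**The case against.** The best defence is that the plan may intend a denominator of recorded months. The line about recorded months sits under the 5.2.2 formula, whose denominator is unspecific, and SAP 9.1.4 limits product-use summaries to available data. That reading is possible, but neither text defines a day count, and the one sentence that does counts all elapsed days. The stray line may equally be left over from 5.2.1. Two programmers could derive different variables.

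The second defence, that the effect is likely small, stands. Sites telephone patients with reminders and collect outstanding forms at V4 (Protocol 7.5.7). Entry requires at least 10 cigarettes a day, about 300 a month. If total use stays near that level, even two gaps leave 300 × 120/180 = 200 of the main product, so in practice only the less-used product can cross a low cut-off.

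A reader might also infer that an early V4 inflates the rate, because the Month 6 form must be completed by V4 (Protocol Appendix 1, footnote c) and V4 may fall on day 180 − 14 = 166. That holds only if the early form carries a full 30-day total: 180/166 = 1.08 from V2. Protocol 7.5.7 collects the form even when its 30-day period would end after V4, which fits a shortened period equally well, giving 166/166 = 1.00. Counted from V1, even a full total gives only 180/173 = 1.04 to 180/180 = 1.00. The documents do not establish the inflation.

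**Conclusion.** As written, SAP 5.2.2 scores a form missing before a later report as zero use, and that rate sets the exposure groups of the primary analysis. The computed rate is 0.83 (one gap) or 0.67 (two gaps) of the true rate with the day count from V2 and the last report at day 180. Counted from V1, one gap gives 0.80 to 0.77, and complete data give 0.96 to 0.93. These figures assume constant use and 30-day forms.

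A reader might go on to infer that the primary grouping is materially wrong. The documents do not support that. Neither the cut-offs nor the rate of missing forms is visible, only count-based classification near a cut-off is exposed, and the number of patients affected is probably small. Percentages and the FAS and PP grouping are untouched. The 5.2.5 fault concerns a covariate only, although the FAS and PP runs reuse the primary model and so carry it too. The point is worth correcting because the primary exposure variable should have one reproducible definition before database lock.

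**What to change.** - In SAP 5.2.2, 5.2.3 and 5.2.5, define the denominator as the days covered by the forms actually received, each day counted once, starting at V2 (Day 1), when allocated product use begins. On the scenarios above this returns 150/150, 120/120 and 60/60 = 1.00.
- Delete the line about index i under the 5.2.2 formula.
- State whether a Month 3 form completed after V3 counts towards V3.
- State how the covered days are derived, since Protocol 7.5.7 mentions a completion date and allows 30-day or calendar months, and say what period an early Month 6 form covers. If it does hold a full 30-day total, counting days once will not remove use reported twice. Its daily rate should then apply only to the days it adds, 166 − 150 = 16 at the earliest V4, giving 166/166 = 1.00.

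The cost is SAP wording and recalculation of the product-use variables from the form dates. A sensitivity run of the primary model without patients who have an earlier gap is optional. The downside is that the rule assumes use in unreported months resembles use in reported months; that is more plausible than assuming none.

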5.2.3 Monthly product consumption

Number of monthly product (HeatSticks, cigarette, other heat not burn products, e-cigarettes, smokeless tobacco pipe, smokeless tobacco, cigars/pipes/kiseru/shisha and nicotine replacement therapy) usage will be defined the daily average (see 5.2.2) multiplied by 30.

$$\left[\text{Monthly product consumption} = 30 * \frac{\text{Total product consumption}}{\text{Total number of days}} \right]$$

5.2.4 Percentage for specific product consumption for dual-users

Percentage for specific product consumption (HeatSticks and cigarettes) will be defined as total consumption of the specific product divided by all product consumption (excluding all other products) from post randomization until date of last self-reported product use.

$$\left[\begin{aligned} &\text{Percentage for specific product consumption to all product consumption (\%)} \\ &= \frac{\text{Total consumption of a given product}}{\text{Total consumption of Heatsticks and cigarettes}} \end{aligned} \right]$$

5.2.5 Average cigarette consumption at V3 and V4.

For each patient regardless of randomized arm, the average daily cigarette consumption at V3 and V4 will be calculated. This will be done as described in section 5.2.2 except that total consumption up to each visit and days elapsed since randomization will be used.

$$\left[\text{Daily product consumption at } V_i = \frac{\text{Total product consumption until } V_i}{\text{Total number of days until } V_i} \right], i = 3, 4$$

where V_3 is Visit 3 and V_4 is Visit 4.

5.3 Urinary Biomarkers

5.3.1 Nicotine Equivalents

The concentration of Neq in spot urine will be derived according to the formula below, and considering the conversion factors described in Table 1. The concentrations reported for free nicotine and its five major metabolites will not be used individually as analysis variables.

Confidentiality Statement

Data and information contained in this document are considered to constitute trade secrets and confidential commercial information, and the legal protections provided to such trade secrets and confidential information are hereby claimed under the provisions of applicable law. No part of this document may be publicly disclosed without the written consent of Philip Morris Products S.A

$$\begin{aligned} \text{Neq [mg/L]} = & (\text{free nicotine}[\mu\text{mol/L}] + \text{nicotine-glucuronide} [\mu\text{mol/L}] \\ & + \text{free cotinine} [\mu\text{mol/L}] + \text{cotinine-glucuronide} [\mu\text{mol/L}] \\ & + \text{free } \textit{trans}\text{-3'-hydroxycotinine} [\mu\text{mol/L}] \\ & + \textit{trans}\text{-3'-hydroxycotinine-glucuronide} [\mu\text{mol/L}]) \\ & *162.2[\mu\text{g}/\mu\text{mol}] / 1000 [\mu\text{g}/\text{mg}] \end{aligned}$$

Table 1: Conversion factors from ng/ml into $\mu\text{mol/L}$

	Molecular weight (g/mol)	Conversion factor from ng/mL to $\mu\text{mol/L}$
Free Nicotine	162.232	0.006164
Nicotine glucuronide	338.356	0.002955
Cotinine	176.218	0.005675
Cotinine-glucuronide	352.341	0.002838
Trans -3'hydroxycotinine	192.217	0.005202
Trans -3'hydroxycotinine-glucuronide	368.34	0.002715

5.3.2 Biomarkers of Exposure adjusted for Creatinine

The adjustment for creatinine for the urinary BoExp will be calculated as:

$$\left[\text{BoExp (creatinine adjusted)} = \frac{\text{BoExp}}{\text{Creatinine}} \right]$$

where the [] indicated concentrations measured from the spot urine collection.

5.3.3 Change from baseline

Mean change from Baseline is the mean of all individual patients' change from Baseline values. Each individual change from Baseline will be calculated by subtracting the individual patient's Baseline value from the value at a given timepoint.

For log-transformed variables, the geometric relative change (RC) from baseline will be calculated,

$$\text{RC} = 100 * (\exp(\text{mean}(\ln(x) - \ln(\text{base}))) - 1)$$

Where $\ln(x)$ is the natural logarithm of the observation and $\ln(\text{base})$ is the natural logarithm

Confidentiality Statement

Data and information contained in this document are considered to constitute trade secrets and confidential commercial information, and the legal protections provided to such trade secrets and confidential information are hereby claimed under the provisions of applicable law. No part of this document may be publicly disclosed without the written consent of Philip Morris Products S.A

of the baseline value.

5.3.4 Coefficient of variation

The geometric coefficient of variation (CV) will be calculated using the following formula:

$$CV = 100\sqrt{e^{var} - 1}$$

where var = the variance from the log-transformed data.

Confidentiality Statement

Data and information contained in this document are considered to constitute trade secrets and confidential commercial information, and the legal protections provided to such trade secrets and confidential information are hereby claimed under the provisions of applicable law. No part of this document may be publicly disclosed without the written consent of Philip Morris Products S.A

6 SAMPLE SIZE JUSTIFICATION

The sample size needed to attain 80% power to show at least a 0.25 mm gain of PD in IQOS user compared to the cigarette user categories as defined in Figure 2, using a one-sided test with 2.5% type I error probability, assuming a dropout rate of 15% and a 10% rate of patients not-adherent to product allocation was 172 patients in total (86 randomized in each arm).

7 CHANGES FROM THE PROTOCOL SPECIFIED STATISTICAL ANALYSES

Changes to “As Exposed Set” to exclude patients with major protocol deviations that affect evaluability of the data. The removal of the “Adherent Use Set” from the analysis sets.

Confidentiality Statement

Data and information contained in this document are considered to constitute trade secrets and confidential commercial information, and the legal protections provided to such trade secrets and confidential information are hereby claimed under the provisions of applicable law. No part of this document may be publicly disclosed without the written consent of Philip Morris Products S.A.

